7.3 Major Hypotheses

(All hypotheses are presented “under the alternative”)

Primary Hypothesis:

On average, participants will have a higher absolute increase in levels of cell-associated HIV RNA transcription in CD4⁺ T-cells seven days after receiving either Pneumococcal or Influenza vaccinations, when compared to seven days after receiving placebo.

Secondary Hypotheses:

- Among the five participants with the largest increases in cell-associated HIV RNA in CD4⁺ T-cells following active vaccination (maximum across all observed time-points), we will deep sequence cell-associated HIV RNA and DNA populations at 0, 2, 4, 7, 14 and 30 days. We hypothesize that active vaccines will *non-selectively* activate cellular transcription of HIV, as evaluated by panmixis tests between sequences of HIV DNA and RNA populations at these sampled timepoints.
- On average, participants will have a greater absolute maximum decrease in levels of total CD4⁺ T-cell-associated HIV DNA measured 2-30 days after receiving either Pneumococcal or Influenza vaccinations, when compared to 2-30 days after receiving placebo.
- Among the five participants with the largest increases in cell-associated HIV RNA in CD4⁺ T-cells following active vaccination (maximum across all observed time-points), we will perform inducible RNA assay. We hypothesize that these five participants will have lower levels of replication competent proviruses 30 days after active vaccination, as compared to their levels of replication competent proviruses sampled before this vaccination.
- Participants will have a greater absolute maximum increase in levels of (a) inflammatory cytokines, (b) T-cell activation and proliferation, (c) HIV-specific immune responses, and (d) vaccine-specific immune responses over the 30 days of observation after receiving either active vaccination, when compared to maximum measures taken over the 30 days of observation after receiving placebo.

- Levels of non-antigen specific immune stimulation (cytokines and general T-cell activation) and vaccine-specific immune responses will be positively associated with increased CD4⁺ T-cell-associated HIV RNA transcription and negatively associated with lower levels of HIV DNA, over the 30 days of observation after receiving either Pneumococcal or Influenza vaccinations.

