15.4 Sample Size Considerations

Examples of Power:

Primary Hypothesis (stated under the alternative): On average, participants will have a higher absolute increase in levels of cell-associated HIV RNA in CD4+ T-cells seven days after receiving either Pneumococcal or Influenza vaccinations, when compared to seven days after receiving placebo. We have chosen to provide estimates of power on the one sampled time point that is likely to show the largest effect, based on our literature review. All other sampled time points following vaccination will be evaluated as well, but to be conservative, we focus on and present power for one sampled time point for our primary hypothesis.

- Assumption: This is a cross-over study with 56 individuals receiving Placebo, Pneumococcus, and Influenza injections in random order (6 possible orders) with sufficient wash-out period in between (minimum 6 weeks) vaccinations. We expect that 6 individuals drop out, resulting in a fully evaluable sample size of 50 individuals. Pilot data were generated from the previous Spanish Study [1] to provide estimates of standard deviations (SD) of change in cell associated HIV RNA levels. From these data, we used a SD of 537 HIV RNA copies/ 10^6 CD4 T-cells for Influenza and 714 for Pneumococcus, and a pooled estimate of 625.
- Effect sizes: In Figure 3, we present the effect sizes that we have 80% power to observe at alpha levels of 0.05 (solid line) and 0.025 (dashed line). Since we will compare observations in the same individual, we will use a paired t-test that compares increases in cell-associated HIV RNA in CD4+ T-cells after 7 days for each of the active vaccine injections (Pneumococcus or Influenza) to 7 days after the placebo injection. For example, if the SD of the differences between active and placebo injection measures is 625 HIV RNA copies/ 10^6 CD4 T-cells, then we will have 80% power at alpha 0.05 to detect an effect size of 253 HIV RNA copies/ 10^6 CD4 T-cells absolute increase or decrease (two-sided test) in cell associated HIV RNA levels following active vaccination versus placebo, which is well-within the range observed in our preliminary data.

Example of Secondary Hypothesis (stated under the alternative): On average, participants will have a greater absolute maximum decrease in levels of total CD4+ T-cell-associated HIV DNA measured 2-30 days after receiving either Pneumococcal or Influenza vaccinations, when compared to 2-30 days after receiving placebo.

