15.8.2 Analysis Plan

All formal analyses of the data will be performed at the end of the study with no real time clinical decisions based on intermediate results. We will utilize a comprehensive AVRC Data Management System developed through our CFAR that can handle all dynamic aspects of clinical research studies including electronic case report form (eCRF) creation and editing, protocol design interfaces, online data entry and QA workflows, real-time accrual monitoring, multi-study data integration, role-based user permissions, integrated specimen processing workflows, an auditing system to track changes to both forms and data, and data visualization and export tools.

Sample and data collection from study participants will occur from study months 6-36 of the study. Unblinding of the study arms for data analysis of primary and secondary endpoints will occur around 44-48 months (after all participants have completed the entire study follow-up), and the final analysis of the trial will take place between 48 and 60 months.

Analysis of the Primary Hypothesis: We will determine whether average changes in levels of cell-associated HIV RNA in CD4+ T-cells are associated with administration of active vaccine or placebo using two-sided paired t-tests with alpha level of 0.05 for each of the two tests (influenza versus placebo and pneumococcus versus placebo).

Secondary analyses: Since subjects will receive multiple injections, we will determine if changes in cell associated HIV RNA in CD4+ T-cell levels are sustained over the weeks following vaccination using graphical and descriptive statistical methods. We will also explore the effect of the vaccines on the size of cell free and cell associated HIV RNA populations using linear mixed effects models and consider incorporating interactions with time to evaluate the change in effects of the vaccines over time.

Additional analyses are described in the Statistical Analysis Plan (SAP).

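### Does the primary hypothesis, worded as an increase after either vaccine, need a multiplicity rule for its two tests at 0.05?

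*Combined protocol and SAP*

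**What the plan says.** The primary hypothesis in section 7.3, repeated in section 15.4, is a higher increase in cell-associated HIV RNA "seven days after receiving either Pneumococcal or Influenza vaccinations, when compared to seven days after receiving placebo". Section 15.8.2 asks whether average changes "are associated with administration of active vaccine or placebo", and answers with "two-sided paired t-tests with alpha level of 0.05 for each of the two tests (influenza versus placebo and pneumococcus versus placebo".

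Section 15.4 describes the same paired t-test, applied "for each of the active vaccine injections (Pneumococcus or Influenza) to 7 days after the placebo injection". It says Figure 3 gives the effects detectable with 80% power at "alpha levels of 0.05 (solid line) and 0.025 (dashed line"; the figure itself is missing from the text available here. The worked example uses 0.05: "if the SD of the differences between active and placebo injection measures is 625" copies per million CD4 T-cells, 253 copies is detectable with 80% power. On time points the section says that "to be conservative, we focus on and present power for one sampled time point for our primary hypothesis".

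The primary endpoint (sections 9.2 and 15.2.1) is defined after each injection. Section 15.8.1.3 rules out a formal interim assessment of efficacy. Section 15.8.2 closes with "Additional analyses are described in the Statistical Analysis Plan (SAP"; that separate plan is not among the documents available here.

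**The concern.** The hypothesis is singular and joins the vaccines with *either*, yet two tests are run, each at the full 0.05 and both against the same placebo cycle. Nothing in the text states how the two results combine, names a familywise error target, orders the tests, or says that no adjustment is intended. Section 15.4 shows 0.025, which is 0.05 divided by 2, but does not explain it, and 15.8.2 does not use it.

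Three readings are open: one win suffices, both are needed, or each vaccine has its own claim. Error and power differ among them. If one win were taken to establish the joint hypothesis, the trial would have two chances of a false claim. The quoted 80% power would then describe neither joint reading.

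**Working it through.** **Inputs.** From section 15.4: 50 evaluable participants, SD of paired differences 625 (537 influenza and 714 pneumococcus, pooled), effect 253, alpha 0.05 and 0.025. From section 15.8.2: two two-sided tests at 0.05. The correlation ρ between the two test statistics is not given. If the three changes have equal variance and are uncorrelated, sharing one placebo change gives ρ = 0.5. I take 0.5 and show 0 to 0.9.

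**The plan's own figure.** The standard error is 625/√50 = 88.4. Solving the noncentral t (49 df) for 80% power gives 252.6 at alpha 0.05, which reproduces 253. At alpha 0.025 it gives 279.7.

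**Error when neither vaccine works.** With a critical value of 1.96 on a bivariate normal:

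- P(both up) = Φ₂(−1.96, −1.96; ρ)
- P(at least one up) = 2 × 0.025 − P(both up)
- P(at least one, either direction) = 1 − P(both statistics within ±1.96)

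| Reading | ρ = 0 | ρ = 0.5 | ρ = 0.9 | Single test |
|---|---|---|---|---|
| One win suffices, increase | 4.9% | 4.5% | 3.5% | 2.5% |
| One win suffices, either direction | 9.75% | 9.1% | 7.0% | 5% |
| Each vaccine its own claim, increase | 2.5% | 2.5% | 2.5% | 2.5% |
| Each vaccine its own claim, either direction | 5% | 5% | 5% | 5% |
| Both must win, increase | 0.06% | 0.46% | 1.5% | 2.5% |

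At ρ = 0.5, for example, 0.05 − 0.0046 = 0.0454.

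**Error when one vaccine works.** The last row is not the worst case for the rule that both must win. If one vaccine has an effect of 253 and the other none, the false both-win rate is about 2.0% at ρ = 0 and 2.5% at ρ = 0.5 and 0.9. That is no more than a single test allows.

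**Power for 253 in both vaccines (SD 625, n = 50).** Each test has 80%. At least one is significant in 91% (96% at ρ = 0, 85% at ρ = 0.9), and both in 69% (64% at ρ = 0, 75% at ρ = 0.9). The 80% per test depends on the pooled SD: it is 90% at 537 and 69% at 714.

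**Cost of adjusting.** Under Holm at familywise 0.05 and ρ = 0.5, power per vaccine falls from 80% to 76% if both work. If only one works, power for it falls from 80% to 71%. Bringing power for 253 back to 80% at alpha 0.025 takes 61 evaluable participants, so 61/0.9 = 67.8, or 68 enrolled, against the planned 50 and 56.

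**Which reading the text supports.** Section 15.8.2 sets alpha per test and names both comparisons. Section 15.4 tests each active injection against placebo, and its 80% is the power of one such test. The endpoint is defined per injection. No section defines a pooled comparison or a claim that one win would establish. The words that point to a joint claim are *either* in the hypothesis and the single question that opens the analysis paragraph.

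**The case for a change.** The strongest case for a change is that the hypothesis as worded is one hypothesis, and a reader could call it met if either test is significant. The single-test error for an increase is then 2.5%, and 4.5% exceeds it at the assumed correlation; the rate stays above 2.5% throughout the range shown. Section 15.4 speaks of an increase or a decrease, so 9.1% against 5% is relevant too. The plan took care to limit the time points to one, but says nothing about the two vaccines. A sentence written before unblinding would cost nothing and would prevent the success rule from being chosen after the results are known.

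Much of this stands. The combination rule is absent from the text available here, the rates reproduce, and the 0.025 line is unexplained. The available text cannot show whether Figure 3 or the separate SAP deals with it.

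The step from there to a needed change does not stand. The inflation arises only under a joint claim based on one win, which the analysis section does not set up. Setting alpha for each of two named tests amounts to choosing not to split it. Correcting across two distinct vaccines, each a question in its own right, is a matter on which statisticians reasonably differ, and here it could cost nine points of power. Quoting the effect detectable at 0.025 would largely repeat what section 15.4 says Figure 3 shows.

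**Conclusion.** No change is needed. An analyst who follows section 15.8.2 runs two prespecified paired t-tests on the day 7 change, each at two-sided 0.05, and reports a result for each vaccine. The error is 5% per claim, and the plan's 80% power for 253 copies holds per test if the SD of the differences is 625. The missing combination rule is a gap in wording that analysts fill sensibly by reporting the two comparisons separately.

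The excess error, 9.1% against 5% in either direction or 4.5% against 2.5% for increases, rests on three conditions: neither vaccine works, the correlation is near the assumed 0.5, and one significant test is presented as proof of a joint claim. A report that made such a claim should be read with those figures in mind.

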16. DATA HANDLING AND RECORDKEEPING

16.1 Data Management Responsibilities

Both archived and prospectively collected and generated data from enrolled subjects will be organized into our central database securely hosted at UCSD, along with all available linked demographic, geographic, clinical, and behavioral data. Confidentiality is maintained by linking data only to the unique ID, and by not storing any personal identifying information in result reporting systems.

16.2 Essential Documents and Access

All essential documents will be maintained by the clinical data manager who will also control permissions and access to the sources documents and essential data.

16.3 Quality Control and Quality Assurance

To ensure an accurate and complete database, key forms will be monitored for discrepancies using automated logical checks. If problems are identified, such as missing clinical data, this will be communicated to study investigators. A Study Status Report including number of participants enrolled or off-study report (list of participants off-study; reasons off-study), SAE report (list of participants; diagnoses), study related AEs \geq grade 3 will be prepared quarterly. Clinical evaluations and specimen collections will be conducted according to the specifications in the study protocol. The study protocol, including materials and informed consent forms, will undergo review and approval by the UCSD IRB and local Ethics Committee prior to implementation, and all participants will be provided with education, counseling and information, and undergo informed consent for all procedures.

17. CLINICAL SITE MONITORING

The National Institute of Allergy and Infectious Diseases (NIAID) contracted site monitors will visit the clinical research site (AVRC) to review participants records, including informed consent forms, CRFs, medical records (e.g., physicians' progress notes, nurses' notes, individuals' hospital charts), and laboratory records to ensure protection of study participants, compliance with the EC/IRB approved protocol/amendments, and accuracy and completeness of records. The monitors will review sites' regulatory files to ensure that local regulatory requirements, in addition to U.S. Federal regulations, are being followed. They will also inspect sites' pharmacies and review product storage, management and accountability records

18. HUMAN SUBJECTS PROTECTIONS

18.1 Institutional Review Board/Ethics Committee

This protocol and the informed consent document and any subsequent modifications will be reviewed and approved by the UCSD Institutional Review Board responsible for oversight of the study. Written informed consent will be obtained from the subject by a member of the study staff. At the time potential subjects contact us regarding the study, any questions they may have will be answered by a member of the study staff. If the potential subject is still interested in participating, a clinic visit will be scheduled. The subject will be informed of the time that needs to be allotted for their first visit in which the informed consent will be administered.

18.2 Vulnerable Participants

18.2.1 Pregnant women and fetuses: Women who are pregnant will be excluded from the study and women who become pregnant while on the study will be asked to complete an early termination visit and will be removed from follow up.

18.3 Informed Consent

18.3.1 Informed Consent Process

Written informed consent (previously approved by UCSD's IRB) explained by trained clinical staff will occur before starting screening procedures. Study entry and administration of the vaccine or vaccine-placebo intervention will occur within 30 days of completion of screening procedures.

The informed consent will describe the purpose of the study, the procedures to be followed, and the risks, and benefits of participation. This information will be explained to the study subject in a face-to-face setting by the individual who consents the participant. Participants will be encouraged to ask questions throughout the consent process and encouraged to discuss their participation with trusted advisors, such as family members, close friends, etc. Participants will be allotted sufficient time to consider whether or not to participate in the research study. After allowing the potential participant time to read the informed consent the study staff and/or investigator will answer and address any questions or concerns the participant may have. Once all questions and concerns have been addressed and the person wishes to participate, they will be asked to sign the informed consent.

Also, during the consent process, the Health Insurance Portability and Accountability Act (HIPAA) Authorization will be addressed. A copy of the consent and HIPAA Authorization form as well as the Notice of Privacy Practices booklet will be given to the subject.

18.3.2 Documentation of Informed Consent

All signed informed consent documents will be kept on file at the AVRC under the supervision of the AVRC regulatory office.

18.3.3 Stored Samples and Associated Data Considerations

18.3.3.1 Data Security: Any data collected as part of this study that is stored at the AVRC and/or is transferred via the internet will follow our data security process as outlined below.

With the fast-developing technology, dependable and comprehensive data security measures are key components to defy the perceived threats of Internet hackers and accidental disclosure of confidential information. In the following we provide a summary of the key features pertinent to this project.

- An anonymous participant identification number is used for all data collection, recording, and submission to the project database.
- Data that contain any participant identifiers (e.g., name or contact information) other than the unique identifier are password protected and accessible only to staff members whose job requires knowledge of such data.

- Laboratories are instructed not to disseminate any participant identifiers in any communications with, or data submissions to, any other AVRC collaborators. Any data transfer over the Internet uses encryption.
- Data transfer and all Web-based utilities use secure access (user and server authentication, 128-bit SSL encryption). This type of encryption is the same as is used for Web-based transactions that involve credit cards or Web banking.

18.3.3.2 Research Laboratory Specimen Identification Policy: All research laboratory specimens leaving the AVRC to an outside laboratory will be de-identified. See the following procedure:

- The Lab Manager will create a study specific AVRC internal lab requisition. The requisition will be saved and accessible via the AVRC internal computer system's shared drive.
- Each research nurse will access and print the study specific requisition(s) via the shared drive.
- Each research nurse will then complete the study specific requisition with the subject's name, DOB, medical record number (MR#), PID, AVRC number and study week.
- The requisition will then be delivered by the research nurse to the AVRC lab.
- The AVRC laboratory staff will then complete the appropriate form for the corresponding laboratory to which the specimen will be sent, using two coded identifiers, the subject's PID number (in the name field) and AVRC number (in the medical record number 's field)
- The AVRC laboratory staff will prepare and label specimen tubes using the same two coded identifiers, the subject's PID number (in the name field) and AVRC number (in the medical record number's field). No personal health identifiers will be included on the specimen label (i.e., no name, initials, DOB, MR#, etc).
- Prior to the blood draw, the phlebotomist will verbally verify the subject's name and DOB. The phlebotomist will confirm the coded specimen tube(s) identifiers with the coded form identifiers.
- Coded specimens are transported to the appropriate lab either by AVRC staff or shipped via FedEx, under IATA regulations.
- All study specific completed AVRC internal lab requisitions will be retained in a locked and secured area for a period of six months and thereafter shredded.
- Samples will be kept frozen and stored for an indefinite length of time.

All stored samples are accessible only to the AVRC laboratory personnel and the appropriate study members. Samples are stored under the coded identifiers as detailed above frozen and in freezers equipped with locks until they are shipped to the central laboratory under contract with the sponsor. The freezers are located in the AVRC and CTF building behind locked doors with cypher or key pad entry.

The stored samples are shipped as outlined above and are then secured under the sponsor's SOPs for storage of human biological samples.

18.4 Risks

Privacy and Confidentiality: Although we will make every effort to protect the subject's privacy and confidentiality it is possible that the subject's status could become known to others. This could cause problems between the subject and the subject's family and/or community and could cause the subject to be discriminated against.

Personal Questions Risks: Subjects will be asked questions about personal issues during this study. There may be questions about their mood, about sexual functioning, about drug use, etc. These types of personal questions may make some subjects uncomfortable.

Reporting Requirements: All cases of HIV, hepatitis B and hepatitis C must be reported to the county public health department. According to California state law, study staff is required to give public health department staff the participant's name, contact information and treatment records for the hepatitis if requested.

Blood Draws: The subject may experience temporary discomfort from the blood draws. The needlesticks may cause local pain, bleeding, bruising and swelling, as well as lightheadedness, dizziness and rarely, blockage of the vein, fainting and/or a local infection.

Vaginal Secretions Collection Risks: Women may have some discomfort or feel embarrassed when they give vaginal fluid sample.

Semen Collection Risks: Men may have some discomfort or feel embarrassed when they give semen sample.

Stool: Subjects may have some discomfort or feel embarrassed when they give stool sample.

Risks of Study Drugs: The drugs used in this study may have side effects, some of which are listed below. Please note that these lists do not include all the side effects seen with these drugs. These lists include the more serious or common side effects with a known or possible relationship. It is very important that subjects tell their study doctor of any changes in their medical condition while taking part in the study. At any time during the study, if subjects believe they are experiencing any of these side effects, they have the right to ask questions on possible and /or known risks. There is a risk of serious and/or life threatening side effects when non-study medications are taken with the study drugs. For their safety, subjects must tell the study doctor or nurse about all medications they are taking before they start the study and must ask approval for taking any new medication while they are on the study.

Risks of Pneumococcal (Pneumovax 23) vaccine: About half of people who get Pneumovax®23 have mild side effects, such as redness or pain where the shot is given. Less than 1% of persons develop a fever, muscle aches, or more severe local reactions. Mild fever, fatigue, headache, chills, and muscle pain have also been reported. Life-threatening allergic reactions are very rare. Serious side effects include: Difficulty breathing, wheezing, rash and hives. These may be signs of an allergic reaction. Participants should contact the study staff immediately if they experience these symptoms.

Risks of Influenza (Fluarix or Fluzone) vaccine: Common side effects include: Low fever, chills, redness or pain where the vaccine was injected, headache, and joint/muscle pain.

Serious side effects include: Severe weakness or unusual feeling in arms or legs, high fever, seizure, convulsions, or unusual bleeding. These may be signs of an allergic reaction. Subjects should contact the study staff immediately if they experience these symptoms.

Inactivated parental vaccine is recommended yearly to all HIV-infected individuals. Vaccination is most effective among persons with CD4 of >100 cells/ μ L and HIV RNA of <30,000 copies/mL, which is in the eligibility requirements for the study. In adults, the most common local and general adverse events after flu vaccine administration were pain and redness at the injection site (20-50%), muscle aches (23%), fatigue (20%), and headache (19%). Vaccination should be avoided by people with known hypersensitivity to any ingredient of the vaccine, and persons previously diagnosed with Guillain-Barré syndrome. Life-threatening allergic reactions from any vaccine are very rare.

Reproductive Risks: It is not known if drug combinations in this study harm unborn babies. If participants are woman and having sex that could lead to pregnancy, they must agree not to become pregnant.

If participant is a woman participating in sexual activity that could lead to pregnancy, she and/or her male partner must use one form of birth control that they discuss with the study staff. Subjects must start one method of birth control before they start taking the study drugs, while they are taking the study drugs, and for 30 days after stopping study drugs.

- Condoms (male or female) with or without a spermicidal agent. Condoms are recommended because their appropriate use is the only contraceptive method effective for preventing HIV transmission.
- Diaphragm or cervical cap with spermicide
- Intrauterine device (IUD)
- Hormone-based contraceptive

Breastfeeding Risk: It is unknown whether the study drugs pass through breast milk and may cause harm to your infant. You must not breastfeed while you are in this study.

Unknown Risks: In addition to the risks listed above, there are risks that are not known or do not happen often when participants have these procedures performed. Participants will be informed in a timely manner, both verbally and in writing of any new information, findings or changes to the way the research will be done that might influence their willingness to continue participating in this study.

